8.1.3 Technical Computational Details for Primary Efficacy Analysis

- 1) CDAI score is the sum of 8 components score multiplying by each component's weight factor. The components of CDAI include: number of liquid or soft stools, abdominal pain, general well-being, presence of complications, taking Lomotil or opiates for diarrhea, presence of an abdominal mass, hematocrit, percentage deviation from standard weight. The formula for CDAI score calculation is: sum of number of liquid or soft stools over a week x 2 + sum of abdominal pain over a week x 5 + sum of general well-being over a week x 7 + presence of complications x 20 + taking Lomotil or opiates for diarrhea x 30 + presence of an abdominal mass x 10 + 6 point per percent deviation of hematocrit from 47% in male and 42% in female + percentage below standard weight x 1. One point each is added for each set of complications which include the presence of joint pains (arthralgia) or frank arthritis; inflammation of the iris or uveitis; presence of erythema nodosum, pyoderma gangrenosum, or aphthous ulcers; anal fissures, fistulae or abscesses; other fistulae; fever during the previous week.
- 2) Remission and none remission subjects (ie, treatment failures) are defined as follows:
 - Subjects who complete the trial and meet the primary endpoint definition at Week 12 without increasing dosages of baseline Crohn's disease medications or taking a new medication for Crohn's disease during the double blind treatment period will be considered as remission subjects for the endpoint.
 - Subjects who increase dosages of baseline Crohn's disease medications or take a new medication for Crohn's disease during the double blind treatment period, or subjects who withdraw from the trial during the

double blind period, in addition to the subjects who fail to meet the primary endpoint at Week 12, will be considered as nonremission subjects for the endpoint.

- 3) If a subject has a Week 12 evaluation but a component of the score is missing, the value of the component in the most recent previous visit will be used for the calculation of the score and the endpoint if no more than 2 components of the CDAI score are missing. CDAI score will be set to be missing if more than 2 components' scores are missing.
- 4) The 3 components of CDAI including liquid or soft stools, abdominal pain and general well-being are collected from the subjects' eDiary. The sum of the scores of the last 7 day's data will be used for each component. If a subject has 1 or 2 days' missing data, the 7 day's score will be calculated by the average of 6 or 5 days' data multiplying 7. If more than 2 days' data are missing, the components' score will set to be missing.
- 5) Clinical remission is defined as CDAI score < 150 for remission subjects as described in session 8.1.1.

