3.7.1.9 Week 12 (+ 2 days)/End of Treatment

The following assessments will occur at Week 12 (around Day 84)/End of Treatment:

- Subjects will complete a daily diary (see [Section 3.7.2.4](#))
- Record the date and time of dose administration in eSource
- Take vital signs (blood pressure, heart rate, body temperature, and respiratory rate)
- Perform a urine pregnancy test for WOCBP (if the urine pregnancy test result is positive, the investigator must follow-up with a confirmatory serum pregnancy test)
- Perform a 12-lead standard safety ECG
- Collect blood samples for PK analysis 1 to 4 hours after the morning dose at the same time as the collection of blood samples for clinical laboratory tests
- Collect blood samples for hematology and serum chemistry, and a urine sample for urinalysis
- Collect a blood sample for the CRP assessment (not needed if CRP is not elevated on Day 1)
- Perform a physical examination (including body weight)
- Determine the CDAI score (for the Week 12 visit, follow the specific assessment as outlined below)
- Collect a fecal sample for the FCP and microbiota assessment (for the Week 12 visit, follow the specific assessment as outlined below)
- All unused IMP will be collected, and final IMP accountability will be performed
- Review and record any concomitant medications
- Assess and record any AEs

The subject must be taking IMP when the following assessments are completed. In order to ensure this occurs, the following schedule must be followed for Week 12 only:

- Collect a fecal sample for the FCP and microbiota assessment approximately 5 days prior to the Week 12 (eg, Day 79) visit date, prior to the bowel preparation and ileocolonoscopy
- Assess the first 3 elements of the CDAI prior to the bowel preparation:
 - Number of liquid or soft stools each day for 7 days
 - Abdominal pain (graded from 0 - 3 on severity) each day for 7 days
 - General well-being, subjectively assessed from 0 (well) to 4 (terrible) each day for 7 days
- The 3-day bowel preparation (consisting of 2 days of dietary modifications and 1 day of cleansing bowel preparation) should be approximately 4 days prior to the Week 12 (eg, Day 80 through Day 82) visit date

Protocol 341-201-00004

- An ileocolonoscopy with biopsy will be conducted up to approximately 1 day prior to the Week 12 (eg, Day 83) visit date. The ileocolonoscopy will be centrally read.
- Determine the SES-CD after the Week 12 ileocolonoscopy has been completed

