8.2.2 Technical Computational Details for Secondary Efficacy Analyses

- 1) Subjects who increase dosages of baseline Crohn’s disease medications or take a new therapy for Crohn’s disease during the trial should be discontinued from the trial, and subjects who withdraw from the trial early are considered as treatment failures in the ITT analysis of the secondary endpoints. These subjects will be considered as non-remission and non-responders for the remission and response endpoints including endoscopic response, PRO-2 remission, clinical response, endoscopic remission.
- 2) For the PRO-2 score used to derive PRO-2 remission, the abdominal pain score is reported as the daily worst abdominal pain (0 to 3) score and the stool frequency score is recorded as the number of loose or watery bowel movements (Bristol stool form scale 6 or 7) per day. The average score of the last 7 day’s data will be used for each component. If a subject has 1 or 2 days’ missing data, the 7 day’s score will be calculated by the average of 6 or 5 days’ data multiplying 7. If more than 2 days’ data are missing, the components’ score will set to be missing.
- 3) No component is allowed to be missing in a PRO related endpoint. PRO-2 remission will be set to missing if either the abdominal pain score or the stool frequency score is missing.

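### The PRO-2 missing-day rule in SAP 8.2.2 compares a weekly figure with per-day cut-offs; separately, the 7-day diary window in SAP 8.1.3 and 8.2.2 has no stated reference day at Week 12

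*SAP*

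**What the plan says.** **PRO-2 scoring.** SAP 8.2.2 item 2 states: "The average score of the last 7 day’s data will be used for each component". When 1 or 2 diary days are missing, the "score will be calculated by the average of 6 or 5 days’ data multiplying 7". With more than 2 days missing, the component is missing, and item 3 then makes PRO-2 remission missing. Remission (Protocol 3.5.2.1, SAP 8.2.1) is a stool frequency of at most 3 per day together with a pain score of at most 1.

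**CDAI scoring.** SAP 8.1.3 item 4 states: "The sum of the scores of the last 7 day's data will be used for each component". It uses the same average-times-7 rule for 1 or 2 missing days. Under item 3, "CDAI score will be set to be missing if more than 2 components" are missing.

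**Week 12 timing.** Neither SAP item says what the 7 days are counted back from. Protocol 3.7.1.9 says "the following schedule must be followed for Week 12 only", and that schedule includes "Assess the first 3 elements of the CDAI prior to the bowel preparation". Footnote n to Protocol Table 3.7-1 repeats the rule. Both places name the CDAI only. The preparation lasts 3 days, "consisting of 2 days of dietary modifications and 1 day of cleansing bowel preparation". The Protocol's example days are 80 to 82 for preparation, 83 for the ileocolonoscopy and about 84 for the visit. For PRO-2, Protocol 7.3.1 and 7.4.2 specify a 7-day average without placing it in time.

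**The concern.** Multiplying by 7 is right for the CDAI, whose diary components are weekly sums. It is wrong for PRO-2, whose components are daily averages with daily cut-offs. A subject who misses a single diary day would be scored on a scale seven times larger than a subject with a complete diary, and would almost always be counted as a non-remitter.

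The window matters for a different reason. Read literally as the week before the Week 12 visit, it takes in the bowel preparation and the ileocolonoscopy. Stools, pain and well-being on those days may reflect the procedure rather than the disease. For the CDAI this would depart from a mandatory Protocol rule on the primary endpoint. For PRO-2 no stated rule would prevent it.

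**Working it through.** The plan gives no figure of its own on this point, so there is nothing to reproduce. The check applies the documents' rules as written.

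**1. PRO-2 with missing days.** Let n be the number of diary days available (6 or 5), S the total loose stools over those days and P the sum of the daily pain scores. Cut-offs are 3 and 1.

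As written, remission needs (S/n) × 7 ≤ 3 and (P/n) × 7 ≤ 1.
- n = 6: S = 2 gives 2.33 (passes); S = 3 gives 3.50 (fails). P = 1 gives 1.17 (fails).
- n = 5: S = 2 gives 2.80 (passes); S = 3 gives 4.20 (fails). P = 1 gives 1.40 (fails).

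On a daily average, remission needs S/n ≤ 3 and P/n ≤ 1.

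| Diary days | Most stools, as written | Most stools, daily average | Largest pain sum, as written | Largest pain sum, daily average |
|---|---|---|---|---|
| 7 (complete) | 21 | 21 | 7 | 7 |
| 6 | 2 | 18 | 0 | 6 |
| 5 | 2 | 15 | 0 | 5 |

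For example, take one loose stool a day and no pain. With 7 days recorded the score is 7/7 = 1, and the subject is a remitter. With 6 days recorded it is (6/6) × 7 = 7, and the subject is a non-remitter.

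**2. Window counted back from the visit.** Take preparation on Days 80 to 82, the procedure on Day 83 and the visit on Day 84.
- Seven days ending the day before the visit: Days 77 to 83. Days 80 to 83 are affected, 4 of 7. Days 77 to 79 remain.
- Seven days ending on the visit day: Days 78 to 84. Days 80 to 83 are affected, again 4 of 7.
- If the visit falls on Day 85 or 86 and preparation moves with it, the count stays at 4 of 7.

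The 4 days are 2 of dietary modification, 1 of cleansing and 1 of procedure.

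**3. Window under the Protocol's CDAI rule.** The last day before preparation is 80 − 1 = 79 and the first day is 79 − 6 = 73. Days 73 to 79 contain no preparation or procedure day.

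**4. Why the window has to be moved and not trimmed.** Blanking the 4 affected days in a visit-anchored window leaves 3 days. Four missing days exceed the limit of 2, so all three CDAI diary components go missing. Three missing components exceed the limit of 2, so the Week 12 CDAI goes missing. PRO-2 goes missing as well.

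**The case against.** **On the CDAI window.** The Protocol already settles it. Section 3.7.1.9 and footnote n require the three diary elements before preparation, and the SAP supplements the Protocol. A programmer working from both would use the right days. This stands: the SAP is silent, not contrary, and what it lacks is a cross-reference. A reader might infer that the SAP overrides the Protocol for the primary endpoint. The text does not support that.

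**On the PRO-2 window.** The intent can be inferred. Protocol 3.7.2.3 builds PRO-2 from two CDAI components, and 3.7.2.4 lists them in one diary set. Section 3.7.2.4 also says that stool frequency from the week of preparation and ileocolonoscopy is not used. A claim that PRO-2 has no window at all would therefore go too far. The gap is narrower but still there: that last sentence is in the screening paragraph, covers stools and not pain, and names no replacement days at Week 12. The Protocol also defers details to a study manual, which was not available.

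**On the affected days.** Two of the four involve dietary change only, and the documents give no figure for the effect of any of them on symptoms. The study days are approximate examples. Both points stand.

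**On the multiplication.** The preceding sentence in the same item calls the score an average, so a careful programmer might see the conflict. That shows the item contradicts itself; it does not say which sentence to follow.

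**Conclusion.** The PRO-2 missing-day rule is wrong as written. It needs no assumption beyond the SAP's own formula and cut-offs: with 1 or 2 missing days, the stool allowance falls from 18 or 15 to 2, and the pain allowance from 6 or 5 to 0.

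The unanchored window is a real but smaller omission. For the CDAI it is a Protocol rule not carried into the SAP; for PRO-2 it is a window that can be inferred but is not stated. The overlap of 4 days in 7 assumes the Protocol's example schedule and a window counted back from the visit.

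Three stronger inferences are not supported.
- **Bias towards an arm.** Both rules apply alike in every arm, so neither favours one by design.
- **A stated loss of power.** That would need the extra stools per subject and the spread of Week 12 CDAI scores, and neither document gives them.
- **An effect on this trial's findings.** SAP section 11 says the planned analyses will not be performed, because the trial ended early with three randomized subjects. In addition, PRO-2 remission is secondary endpoint #3 and would be formally tested only after every earlier step in SAP 8.4 had succeeded.

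This is a defect of the plan as written, worth correcting in the text.

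**What to change.** 1. In SAP 8.2.2 item 2, delete the multiplication by 7, so that with 1 or 2 missing days PRO-2 is the daily average over the 6 or 5 available days. Leave the rule in 8.1.3 item 4 as it is, since the CDAI components are weekly sums.
2. In both items, define the Week 12 window as the 7 consecutive diary days ending the day before that subject's first bowel-preparation day (for example, Days 73 to 79). Where no preparation took place, use the 7 days ending the day before the visit.
3. Apply the limit of 2 missing days inside that window.
4. Cite Protocol 3.7.1.9 and state that the window applies to both CDAI and PRO-2.

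The cost is wording in two SAP items, one cross-reference and one programming rule. The daily diary already covers Days 73 to 79, so no visit, procedure, sample size or alpha changes.

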8.1.4 Sensitivity Analyses

8.1.4.1 Placebo-based Pattern Imputation

A sensitivity analysis of the primary endpoint of clinical remission of missing data will be provided for subjects who withdraw from the trial before the Week 12 visit , or subjects who increase dosages of baseline Crohn's disease medications or take a new medication for Crohn's disease during the double-blind treatment period. The missing data under this scenario is considered as Missing Not at Random (MNAR) and will be imputed. A pattern-mixture model approach will be utilized to model the distribution of the observed responses and the distribution of the missing responses using a placebo-based multiple imputation(MI). Imputation of missing CDAI scores will be produced using a regression approach¹ and the imputed CDAI remission status will be determined by checking if the imputed CDAI score is less than 150.

Specifically, the placebo-based pattern imputation procedure follows these steps:

- 1) Using Monte Carlo Markov Chain (MCMC) methodology from PROC MI by treatment group to impute the intermittent missing data to a monotone missing pattern;

- 2) Using pattern-mixture model approach to impute the monotone missing data. By applying MNAR statement of PROC MI in SAS, missing values under MNAR will be imputed. Only the observations in the placebo control group will be used to impute the missing values by using the MODEL option in the MNAR statement. The imputed values for the 3 treatment groups of OPS-2071 will be adjusted using the shift parameter. When the shift parameter is 0, the MI procedure would produce an analysis which is essentially something called “back to placebo”;
- 3) For subjects with imputed CDAI scores, CDAI remission status will be determined by checking if CDAI score < 150;
- 4) Using logistic regression model in the primary analysis to analyze the completed data along with the imputed data;
- 5) Obtaining the overall results using PROC MIANALYZE.

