7.4.1.1 Sensitivity of the Primary Endpoint

A sensitivity analysis of the primary endpoint of clinical remission of missing data will be provided for subjects who withdraw from the trial before the Week 12 visit, or subjects who increase dosages of baseline Crohn's disease medications or take a new medication for Crohn's disease during the double-blind treatment period. A pattern-mixture model approach will be utilized to model the distribution of the observed responses and the distribution of the missing responses using a placebo-based multiple imputation. Imputation of missing CDAI scores will be produced using a regression approach¹⁷ and the imputed CDAI remission status will be determined by checking if the

Protocol 341-201-00004

imputed CDAI score is less than 150. Details of this sensitivity analysis will be provided in the statistical analysis plan (SAP).

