3.3 Trial Population

Approximately 240 male and female subjects between the ages of 18 and 70 (inclusive), with Crohn's disease and showing symptoms of active inflammation despite ongoing

treatment, will be randomized. Active mucosal inflammation will be confirmed by centrally read ileocolonoscopy. Discontinued or withdrawn subjects will not be replaced.

4 Sample Size

For the primary endpoint of clinical remission (CDAI score < 150), assuming a 40% response rate in the OPS-2071 600 mg BID and 300 mg BID dose groups and a 20% response rate in the placebo group, 60 randomized subjects per treatment group would provide 80% power to detect a treatment difference between the OPS-2071 pooled dose groups (600 mg BID and 300 mg BID) and the placebo group in the primary endpoint, using a 2-sided alpha of 0.05. The total sample size of the trial is 240 randomized subjects with 1:1:1:1 randomization to OPS-2071 600 mg BID, 300 mg BID, or 150 mg BID, or placebo BID. The power of individual dose comparison with placebo under the same assumption is 67%.

For the secondary endpoint of endoscopic response, assuming a 26.5% response rate in the OPS-2071 600 mg BID and 300 mg BID dose groups and a 10% response rate in the placebo group, 60 subjects per treatment group would provide 80% power for the comparison between the OPS-2071 pooled dose groups (600 mg BID and 300 mg BID) and the placebo group, and 65% power for the individual dose comparison with placebo, using a 2-sided alpha of 0.05.

5 Statistical Analysis Datasets

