8.1.1 Primary Estimand

The primary objective is to investigate the therapeutic effect of OPS-2071 add-on therapy administered orally for 12 weeks in subjects with Crohn's disease showing symptoms of active inflammation despite ongoing treatment. The primary estimand defining the treatment effect of interest in the protocol uses a mixture of composite strategy and treatment policy strategy specified in the ICH E9 addendum.² Two types of intercurrent events are accounted for by these two strategies:

- Increasing dosages of baseline Crohn's disease medications or taking a new therapy for Crohn's disease: The occurrence of this intercurrent event may provide meaningful information on the treatment effect of interest such as lack of efficacy, and will be taken to be a component of the variable for the primary estimand. Following the composite strategy, the primary estimand assess the treatment effect based on a composite variable which combines percentage of subjects achieve clinical remission at week 12 and the intercurrent event of the changes of the medications for Crohn's disease. The subjects with this type of intercurrent event will be considered as treatment failures.

- Early withdrawal from the trial: Interest lies in the treatment effect regardless of this intercurrent event. Following treatment-policy strategy, occurrence of the early withdraw intercurrent event is ignored, and the primary estimand is then the difference between treatment groups in percentage of subjects who achieve clinical remission at week 12, regardless of whether or not early withdraw had occurred.

The primary estimand for this trial is defined by the following components:

- Population: subjects with Crohn's disease and showing symptoms of active inflammation despite ongoing treatment who have met the protocol-defined inclusion/exclusion Criteria
- Endpoint: the percentage of subjects who, at Week 12, achieve clinical remission (defined as a CDAI score < 150)
- Intercurrent Events: increase dosages of baseline Crohn's disease medications or take a new therapy for Crohn's disease during the trial, and early withdraw from the trial
- Population-level summary: difference in clinical remission proportions between OPS2071 and placebo

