A sensitivity analysis of secondary endpoint #3 (PRO-2 remission) of missing data will also be provided similar to the sensitivity analysis of the primary endpoint of CDAI clinical remission. Specifically, missing data for PRO-2 remission will be imputed for the subjects who withdraw from the trial before the Week 12 visit without increasing dosages of baseline Crohn's disease medications or taking a new medication for Crohn's disease during the double-blind treatment period. The missing data under this scenario is considered as MNAR and will be imputed by applying a regression approach¹ to the abdominal pain and stool frequency scores, averaged over a 7-day period. In detail, the placebo-based pattern imputation procedure follows these steps:

- 1) Using Monte Carlo Markov Chain (MCMC) methodology from PROC MI by treatment group to impute the intermittent missing data to a monotone missing pattern;
- 2) Using pattern-mixture model approach to impute the monotone missing data. By applying MNAR statement of PROC MI in SAS, missing values under MNAR will be imputed. Only the observations in the placebo control group will be used

to impute the missing values by using the MODEL option in the MNAR statement. The imputed values for the 3 treatment groups of OPS-2071 will be adjusted using the shift parameter; When the shift parameter is 0, the MI procedure would produce an analysis which is essentially something called “back to placebo”;

- 3) The PRO-2 remission status for the subjects with the imputed data will be determined by checking if the imputed stool frequency score is ≤ 3 and the imputed abdominal pain score is ≤ 1 ;
- 4) Using logistic regression model in the primary analysis to analyze the completed data along with the imputed data;
- 5) Obtaining the overall results using PROC MIANALYZE.

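### The primary endpoint's sensitivity analysis imputes subjects whom the primary estimand already counts as failures, so it addresses a different estimand and its result moves with rescue imbalance in either direction

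*SAP*

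**What the plan says.** "Rescue" below is shorthand for increasing a baseline Crohn's medication or taking a new Crohn's therapy.

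- **Estimand.** SAP 8.1.1 assigns rescue to the composite strategy: "The subjects with this type of intercurrent event will be considered as treatment failures". The end of 8.1.1 and item 2 of SAP 8.1.3 repeat that such subjects are failures or nonremission.
- **Sensitivity analysis, primary endpoint.** SAP 8.1.4.1 covers subjects who withdraw before Week 12 and also rescued subjects. It states: "The missing data under this scenario is considered as Missing Not at Random (MNAR) and will be imputed". CDAI is imputed from placebo observations, with a shift parameter for the active arms that has no stated value. Step 3 sets remission by CDAI below 150, and step 4 fits the primary logistic model. Neither step returns rescued subjects to failure.
- **Protocol.** Section 7.4.1.1 begins "A sensitivity analysis of the primary endpoint of clinical remission of missing data will be provided for subjects who withdraw from the trial" and goes on to add rescued subjects. The SAP follows it.
- **Sensitivity analysis, PRO-2.** SAP 8.2.1 calls this similar to the primary one but gives a narrower scope: "missing data for PRO-2 remission will be imputed for the subjects who withdraw from the trial before the Week 12 visit without increasing dosages" or taking a new Crohn's medication.
- **Missing-data text.** Protocol 7.3.1 and SAP 5.2 describe Week 12 data after a medication change as missing and handled by failure status. Data collected after the change go to listings only.

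**The concern.** Under a composite strategy the event is part of the outcome. A rescued subject's remission status is known, whatever CDAI might have been at Week 12. Imputing a CDAI for that subject and allowing remission replaces the composite outcome with a hypothetical one: what the score might have been under a placebo-like course. Rescued subjects are encouraged to stay in the trial, so an observed Week 12 CDAI may even exist and be set aside in favour of a draw from the placebo model.

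A sensitivity analysis should vary an assumption while holding the estimand fixed. This one changes the missing-data assumption for withdrawals and the estimand for rescued subjects together. If it disagreed with the primary result, the reader could not tell from that output which change was responsible. No other planned analysis separates them: the Cochran-Mantel-Haenszel analysis in SAP 8.1.5 uses the primary endpoint as defined, and no withdrawal-only version is planned for CDAI remission.

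**Working it through.** **Inputs from the documents (SAP Section 4, Sample Size; same in Protocol 7.1).** Remission 40% on 600 mg and 300 mg ("assuming a 40% response rate in the OPS-2071 600 mg BID and 300 mg BID dose groups") and 20% on placebo ("a 20% response rate in the placebo group"); 60 per arm, so 120 pooled against 60; two-sided alpha 0.05.

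**Inputs not in the documents, assumed.** Rescue shares r_A (active) and r_P (placebo). Imputed remission probability q for a rescued subject, set at a fraction f = 25%, 50% or 100% of the remission rate among non-rescued placebo subjects. Shift zero, so q is the same in all arms. No withdrawals, so that rescue is the only thing that moves.

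**Step 1: the plan's own figure.** Power = Φ((|A − P| − 1.96·s0)/s1), where s0 is the pooled-variance standard error and s1 the unpooled one.
- Pooled doses, 120 vs 60: mean rate 0.333, s0 = 0.0745, s1 = 0.0683; (0.20 − 0.1461)/0.0683 = 0.789, so power is 78.5%. The plan states 80%; an exact chi-square calculation gives 79.2%.
- Single dose, 60 vs 60: s0 = 0.0837, s1 = 0.0816; power 67.0%. The plan states 67%.

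The plan's figures are reproduced to within two points.

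**Step 2: effect of imputing rescued subjects.** In the composite analysis they contribute no remitters. After imputation:
- P = 0.20 + r_P·q and A = 0.40 + r_A·q
- difference = 0.20 − q·(r_P − r_A)
- q = f × 0.20/(1 − r_P)

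The difference shrinks when placebo has more rescue, is unchanged when rescue is equal, and grows when active has more.

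**Step 3: numbers.** Power uses the Step 1 formula at the new rates, without the extra variance from imputation.

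| Rescue, active / placebo | f | q | A | P | Difference (points) | Power |
|---|---|---|---|---|---|---|
| Composite analysis | – | – | 40.0% | 20.0% | 20.0 | 78.5% |
| 10% / 25% | 25% | 6.7% | 40.7% | 21.7% | 19.0 | 73% |
| 10% / 25% | 50% | 13.3% | 41.3% | 23.3% | 18.0 | 67% |
| 10% / 25% | 100% | 26.7% | 42.7% | 26.7% | 16.0 | 56% |
| 15% / 15% | 100% | 23.5% | 43.5% | 23.5% | 20.0 | 76% |
| 25% / 10% | 25% | 5.6% | 41.4% | 20.6% | 20.8 | 81% |
| 25% / 10% | 100% | 22.2% | 45.6% | 22.2% | 23.3 | 88% |

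**Step 4: imputation variance.** A simulation applied Rubin's rules (3,000 trials per scenario, 30 imputations, unadjusted log odds ratio, remission imputed as a binary outcome). It counted significant composite results that became non-significant, with q at half and at all of the observed placebo rate.
- Equal rescue of 10% or 20%: 3% to 13%.
- 10% active / 30% placebo: 30% to 56%.
- 20% active / 10% placebo: about 1%.

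**Step 5: with the scope corrected.** If rescued subjects stay nonremission and there are no withdrawals, the analysis returns the composite result, 40% vs 20% and 78.5% power, whatever the rescue rates.

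**The case against.** The strongest reply is that the plan treats these data as missing on purpose. Protocol 7.3.1 and SAP 5.2 attribute missing Week 12 data to medication change as well as to withdrawal and present failure status as the way it is handled. On that reading, nonresponder status is a missing-data rule and SAP 8.1.4.1 stress-tests it. Protocol and SAP agree on the scope, so it is not a drafting drift between them. This stands in part: a reader might infer that the plan nowhere regards these data as missing, and that is wrong. But SAP 8.1.1 names the composite strategy for this event, and its closing paragraph ties missing data to withdrawal alone. The documents hold two framings, and only one matches the stated estimand. The mismatch with PRO-2 does not by itself show which scope was intended; the composite definition does.

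Second, the size may be small. A regression imputation that uses earlier CDAI values would give low remission probabilities to subjects rescued after doing badly. This stands, and is why a range is shown; 16.0 points and 56% power are the top of the range for q, not a central estimate. A non-zero shift would also change the size.

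Third, power is a weak yardstick, because the plan sets no significance requirement for this analysis. That also stands. The figures show how far the output can move, not a loss of power for the trial.

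**Conclusion.** The point holds as an estimand mismatch, and that conclusion needs no assumed number: SAP 8.1.1 fixes rescue as failure, while SAP 8.1.4.1 and Protocol 7.4.1.1 let rescued subjects become remitters. The size rests on assumed rescue rates, imputed remission probability and shift.

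Three stronger readings are not supported.
- A reader might infer a general bias toward no effect. The direction depends on which arm has more rescue, and the documents give no rates.
- A reader might infer that any discrepancy would come from rescue imbalance alone or could never be interpreted. The analysis also imputes withdrawals, and imputation variance changes some results even with equal rescue. A withdrawal-only run would separate the sources, but none is planned.
- A reader might infer that the primary conclusion is at risk. The primary test and the gatekeeping in SAP 8.4 do not use this analysis, so type I error control is unaffected.

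Imputing withdrawals is not the problem. SAP 8.1.1 labels withdrawal treatment policy but scores it as failure, so a missing-data check there is appropriate. SAP Section 11 reports early termination with three randomized subjects and says the planned analyses will not be performed. No reported result is affected; the point concerns the plan's text and any reuse of it.

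**What to change.** In SAP 8.1.4.1 and Protocol 7.4.1.1, keep subjects with a medication increase or new Crohn's therapy as nonremission in every imputed data set. Impute only subjects who withdraw before Week 12 without such a change, which is the scope SAP 8.2.1 uses for PRO-2. If non-rescued completers whose CDAI is set to missing under the more-than-two-components rule are also to be imputed, state that as a separate extension, since SAP 8.2.1 does not cover such subjects.

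Align Protocol 7.3.1 and SAP 5.2 with the composite definition, so that rescue is described as an outcome and not as a source of missing data.

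If the present version is kept, label it a supplementary analysis, state its hypothetical estimand, and add the withdrawal-only analysis as the sensitivity analysis.

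The cost is one clause in each sensitivity section and a matching sentence in each missing-data section. No design, data collection or sample size change is needed.
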